5.1 Site Selection

The trial sponsor has overall responsibility for site and investigator selection and has delegated this role to the CI and NCTU.

5.1.1 Study Setting

Participant recruitment will be from stroke centres in NHS trusts, within wards and community hospitals across the UK.

The trial has been designed to allow T1 and T2 assessments to be delivered where the patients are discharged to (e.g., own homes) avoiding additional travel to hospital settings and thus reducing the burden on participants. Baseline assessments and interventions are delivered while the patient is within hospital settings to maximise controlled conditions and avoid additional travel to hospitals or transfer by ambulance for MRI.

Both sites with and without MRI can participate as only a subsample of patients (80) are required to meet the target for the MRI mechanistic sub study.

5.1.2 Site/Investigator Eligibility Criteria

To participate in the SIGHT trial, investigators and trial sites must fulfil a set of criteria that have been agreed by the SIGHT Trial Management Group (TMG) and that are defined below.

Trial sites meeting eligibility criteria will be issued with the SIGHT local information pack needed by the Research and Development Department (R&D) of their Trust to enable the Trust to provide confirmation of capacity and capability to undertake the study.

Some sites for this study have been preselected based on their ability to recruit sufficient participants to the trial and/or having an interested principal investigator. The following sites will be included: Norfolk and Norwich University Hospital; Cambridge University Hospital; Imperial College Healthcare Trust; Salford Royal Hospital; Nottingham University Hospital; and Birmingham Community Healthcare Trust. To achieve our target, we will need at least 8 acute and 8 community centres and as such additional sites will need to be opened.

5.1.2.1 Principal Investigator's (PI) Qualifications and Agreements

The investigator(s) must be willing to sign an investigator statement to comply with the trial protocol (confirming their specific roles and responsibilities relating to the trial, and that their site is willing and able to comply with the requirements of the trial). This includes confirmation of appropriate qualifications, familiarity with the appropriate use of any investigational products, agreement to comply with the principles of GCP, to permit monitoring and audit as necessary at the site, and to maintain documented evidence of all staff at the site who have been delegated significant trial related duties.

5.1.2.2 Resourcing at site

The investigator(s) should be able to demonstrate a potential for recruiting the required number of suitable participants within the agreed recruitment period (i.e., the investigator(s) regularly treat(s) the target population). They should also have an adequate number of qualified staff and facilities available for the foreseen duration of the trial to enable them to

conduct the trial properly and safely including separate staff for delivery of assessments and intervention. The minimum expected per site:

- Demonstrate a potential for recruiting the required number of suitable participants within the agreed recruitment period (i.e., the investigator(s) regularly treat(s) the target population)
- A named clinician is willing and appropriate to take Principal Investigator responsibility
- Suitably experienced and trained staff are available to recruit participants, enter data and undertake trial procedures as detailed in this protocol:
 - Trained staff who can deliver the baseline assessments and intervention
 - Trained staff who can deliver the blinded assessments at T1 and T2 (including outside of recruiting hospital, e.g., patients' own homes)
- The site should have a separate room to deliver the SIGHT intervention
- The site should have space to store the assessment and therapy materials
- Site team willing and able to take steps to avoid unintentional unblinding on patient files or Electronic Health Records (EHR) system (e.g., not record SIGHT intervention delivery on patient notes)
- The site should have sufficient data management resources to allow prompt data
 return to NCTU

Optional

 Sites able to deliver the (optional) CENT measure should have access to a 40inch TV screen and be able to have patients approximately 170cm away from this to complete the test. Additionally, sites should have access to a laptop to run the CENT application on, a HDMI cable to connect the laptop to the screen, and a mouse for the participant to use. UEA will provide the CENT measure free of charge.

For sites participating in mechanistic MRI sub study only:

• the site should have sufficient access to a 3T MRI scanner and be able to deliver the sequences listed in this protocol (T1, T2-Flair, DTI and rsfMRI)

Sites will be expected to complete a delegation of responsibilities log and provide staff contact details. The local site team should communicate changes in staff, delegated to undertake activities for the SIGHT trial, to the trial team. Further trial specific training of local site staff will be provided by NCTU as necessary.

The site should have sufficient data management resources to allow prompt data return to NCTU.

5.1.2.3 Training for staff on recruitment and baseline and follow-up assessments

Training for recruitment will be provided by the NCTU and members of the research team. Initial training will be provided during the start-up phase of the trial and staff undertaking recruitment will be required to maintain a current Good Clinical Practice certificate. Online videos and textual resources will be available to recruiting staff throughout the trial.

Research staff will be trained in delivering the baseline and outcome assessments. Blinding of assessors for complex interventions such as the SIGHT intervention can be challenging due to site resources and unintended feedback from patients. Where possible, baseline measures and randomisation will be undertaken by staff separate to those staff in

undertaking the outcome measures at T1 and T2 timepoints. For T1 and T2, assessors will be requested to indicate whether they have been unblinded to the treatment arm prior to starting the measures.

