5.1.2.4 Training for Staff delivering the SIGHT Intervention

Site staff will be trained to deliver the intervention. This training will comprise of a therapy manual and video supported by online/in person training. The intervention may be delivered by staff undertaking baseline measures and randomisation, but not outcome measures at T1 and T2 timepoints. We will follow a 'train-the-trainer approach' with one lead therapist at each site being trained to be able to train new staff coming into the trial.

Following training, site staff will be asked to demonstrate competency in applying SIGHT. Catch-up meetings with site intervention delivery teams will help to address any issues with delivery and discuss the importance of reducing risk of contamination. A fidelity checklist will be completed at the first and last session and will be monitored by the central team, and intervention delivery teams will be contacted about deviations. No formal education in stroke care is required to deliver SIGHT, as the intervention is easy to administer. The lead therapist at each site will be asked to randomly check throughout the trial if the intervention is being delivered as per protocol by SIGHT therapists.

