5.5.2.4 Measures of Treatment As Usual (TAU)

TAU will be captured in two ways.

At **site level**, the **profile of TAU** (e.g., average neglect therapy time, frequency, type of therapy and location) will be recorded by the senior stroke occupational therapist at each centre at start of recruitment when the site opens, during the recruitment period, and at end of recruitment.

At **individual patient level**, the therapy delivery staff will record the frequency, duration, location, and overall content (e.g., visual and scanning therapies) of each TAU session the participant receives during the 10-day period of intervention using a study-specific therapy booklet placed in the patient's bedside developed with clinical teams and adapted from our c-SIGHT and SPATIAL feasibility studies.

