5.9.2 Blinding

The research staff delivering therapy at each site will be notified of group allocation via the NCTU secure web-based service. Group allocation will be withheld from the blinded assessors. To reduce the risk of contamination, SIGHT will be delivered in a separate treatment room and onsite monitoring of intervention delivery will review trial progress and discuss the importance of this risk. Blinded assessors will only conduct assessments at follow-up visits T1 and T2.

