5.9.3 Unblinding

While every effort will be made to ensure that site staff undertaking the efficacy assessments remain unblinded, these staff will be asked to record any occurrences of unblinding.

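### Separating the staff who take baseline and randomise from the T1/T2 assessors is only conditional in section 5.1.2.3, which conflicts with the unconditional blinding rule in 5.9.2 and the assessor-blind design in 4.3

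*Protocol*

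**What the plan says.** **Who may assess.** Section 5.1.2.3 sets the staffing rule for assessments: "Where possible, baseline measures and randomisation will be undertaken by staff separate to those staff in" undertaking the T1 and T2 outcome measures. The sentence before it gives the reason for the caution: "Blinding of assessors for complex interventions such as the SIGHT intervention can be challenging due to site resources and unintended feedback from patients". Section 5.1.2.4 adds a firm bar for one group: "The intervention may be delivered by staff undertaking baseline measures and randomisation, but not outcome measures at T1 and T2 timepoints". Section 5.1.2.2 lists the minimum resources per site. Staff for baseline and intervention are one item, and the next item is "Trained staff who can deliver the blinded assessments at T1 and T2".

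**Blinding.** Section 5.9.2 is unconditional on both counts: "Group allocation will be withheld from the blinded assessors", and "Blinded assessors will only conduct assessments at follow-up visits T1 and T2". Section 4.3 describes the design as assessor-blind. Section 5.9.3 states that every effort will be made to "ensure that site staff undertaking the efficacy assessments remain unblinded", and asks those staff to record any unblinding.

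**Who is told the arm.** Section 4.3 has therapy delivery staff notified, and withholds allocation from the rest of the trial team, from recruiting staff and from assessors. Section 5.6.1.3 has the database notify the trial team as well as the local delivery staff. Section 5.9.1.3 has an email go to the research team members assigned to the patient, who are not further defined. Section 5.4.3 has the database alert NCTU operations and relevant site staff, again undefined, both to Arm B allocations and to follow-up visits falling due.

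**The concern.** A site that follows 5.1.2.3 may let one person take baseline, trigger randomisation and later score T1, provided it judges separation not possible. A site that follows 5.9.2 may not. The conditional rule sits in the section that sites will use to train and roster assessors, so it is likely to be the one applied.

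Section 4.1.1 explains that the sham was dropped because of attrition and that the comparator is usual care. Participants given SIGHT know they are doing rod training, and assessor blinding is the only masking the design claims. If an assessor knows the arm, the way a test is introduced, prompted or ended can differ between arms, and so can an observer's rating. Such bias would be expected to favour SIGHT.

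**Working it through.** The plan states no figure on this point, so the check is a comparison of the text. Take a site nurse who collects T0, submits the baseline forms that enable randomisation, and delivers no SIGHT sessions.

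**Step 1. May this nurse score T1 or T2 for that participant?**

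| Protocol section | Answer |
|---|---|
| 5.1.2.3 | Yes, where separation is judged not possible |
| 5.1.2.4 | Not barred; the bar covers only those who deliver SIGHT |
| 5.1.2.2 | Lists two staffing items, but does not say that nobody may do both baseline and follow-up |
| 5.9.2 | No; blinded assessors do T1 and T2 only |

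Sections 5.1.2.3 and 5.9.2 give opposite answers, and neither of the other two sections closes the gap.

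**Step 2. Could this nurse know the arm?**

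| Protocol section | Answer |
|---|---|
| 4.3 | No, if counted among recruiting staff or other trial team members |
| 5.6.1.3 | Yes, if counted as part of the trial team |
| 5.9.1.3 | Open; depends on who the assigned research team members are |
| 5.4.3 | Open; depends on who the relevant site staff are |
| 5.9.2 | Names only the blinded assessors as the people from whom allocation is withheld |

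Section 4.3 would keep the nurse blind. The other sections do not guarantee it.

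**Step 3. Combine.** Steps 1 and 2 together allow a person who has been told the arm to score outcomes. They do not show that this will happen at any given visit.

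**Step 4. Do the safeguards prevent it?** Section 5.1.2.3 asks assessors, before they start, whether they have been unblinded, and 5.9.3 asks them to record occurrences. Both document a breach without preventing one. Withholding news of delivery delays (5.4.2.1) and holding separate check-in meetings (5.4.4) limit leakage from therapists to assessors. Neither applies to someone who was told the arm directly.

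**Step 5. Which outcomes are exposed?** CBS KF-NAP (5.5.2.1) is a clinician's rating of observed self-care activities, so no participant-marked sheet exists from which it could be scored again. Star Cancellation (5.5.1) is a paper-and-pencil test. Section 5.10.1 provides for blinded scoring of paper assessments and for copies to be uploaded. That protects the count of cancelled stars, but not the way the test was administered.

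**The case against.** The strongest reply is that taking part in randomisation is not the same as knowing the arm. Randomisation is web-based, 4.3 withholds allocation from recruiting staff, and the people who certainly know the arm, those delivering SIGHT, are barred outright from T1 and T2. Knowing a participant's baseline score does not reveal allocation either. All of this stands, and it limits the point to a permitted risk. It does not remove it, because the notification sections do not keep to the rule in 4.3.

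A second reply is that 5.1.2.2 already separates the two teams, so only wording is at issue. That supports the view that separation is intended and makes the fix cheap. But the section lists capabilities without excluding overlap, and 5.1.2.3 then makes the separation conditional.

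A reader might be tempted by stronger readings that the documents do not support:

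- *The person who randomises is told the arm.* No section says so. Sections 5.6.1.3 and 5.9.1.3 only leave it open.
- *The "study-specific therapy booklet placed in the patient's bedside" discloses the arm to the assessor.* Section 5.5.2.4 describes it as a record of usual-care sessions, and 5.6.1.4 has usual care recorded in both arms. Nothing says that SIGHT is entered there, and 5.1.2.2 asks sites to keep SIGHT delivery out of patient notes.
- *Assessor masking is the only protection against biased scoring.* Section 5.10.1 gives the paper tests a further one.
- *Section 5.9.3 plans for unblinded assessors.* Read with its own request to record unblinding and with 5.9.2, the word is an evident slip.

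**Conclusion.** The contradiction between 5.1.2.3 and 5.9.2 is real, and the notification rules in 4.3, 5.6.1.3 and 5.9.1.3 do not agree. Taken together, the protocol permits outcome assessment by someone who knows the arm in a trial whose only stated masking is of assessors. It does not make this certain. Exposure is greatest for the secondary CBS KF-NAP and smaller for the primary Star Cancellation.

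No magnitude can be given. The documents state neither how often an assessor would know the arm nor how far a score would move if so. A reader might supply values for both and convert them into a bias or an inflated false-positive rate, but the result would be pure assumption. It would also mix in unblinding through patients' remarks, which 5.1.2.3 itself names and which separating staff would not prevent. The conclusion rests on the wording alone. The change is worth making because it costs little and follows the protocol's own intent.

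**What to change.** - **Section 5.1.2.3:** delete the condition. State that anyone who took baseline, randomised, received the allocation notice or delivered SIGHT for a participant may not assess that participant at T1 or T2. Leave the bar on SIGHT deliverers in 5.1.2.4 as it is, and word 5.9.2 to match.
- **Sections 5.6.1.3 and 5.9.1.3:** align them with 4.3, so that the only people at the site told the allocation are the SIGHT delivery staff. In 5.4.3, make clear that reminders of follow-up visits sent to assessors carry no allocation.
- **Section 5.9.3:** correct the text to say that efficacy assessors remain blinded.

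If the sponsor needs to keep the exception, 4.3 and 5.9.2 must state it openly.

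**Cost:** a protocol wording change and slightly less rota flexibility, felt most at small sites. No staff are added. Sections 5.1.2.2 and 5.1.2.4 already require SIGHT deliverers and T1/T2 assessors to be different people, and 5.1.2.4 lets the deliverers do baseline and randomisation. The two groups a site must already have can therefore cover every task.

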5.1.2.4 Training for Staff delivering the SIGHT Intervention

Site staff will be trained to deliver the intervention. This training will comprise of a therapy manual and video supported by online/in person training. The intervention may be delivered by staff undertaking baseline measures and randomisation, but not outcome measures at T1 and T2 timepoints. We will follow a 'train-the-trainer approach' with one lead therapist at each site being trained to be able to train new staff coming into the trial.

Following training, site staff will be asked to demonstrate competency in applying SIGHT. Catch-up meetings with site intervention delivery teams will help to address any issues with delivery and discuss the importance of reducing risk of contamination. A fidelity checklist will be completed at the first and last session and will be monitored by the central team, and intervention delivery teams will be contacted about deviations. No formal education in stroke care is required to deliver SIGHT, as the intervention is easy to administer. The lead therapist at each site will be asked to randomly check throughout the trial if the intervention is being delivered as per protocol by SIGHT therapists.

5.1.2.5 MRI site set-up

MRI set-up support will be provided to sites by the MRI physicist. Local MRI support at each site will work with the central support to modify/develop the required sequences, which will be matched as closely as possible to other sites accepting that there will be differences based of scanner manufacturer/model. Set-up scans on healthy volunteers (same person at each site, where possible) will be performed and analysed to determine that a) scans are of acceptable quality and b) the quantitative results are consistent with other sites. Once this process is completed, approval of the MRI protocol will be given by the central MRI physicist.

At sites with ethical approval for imaging healthy volunteers for the purpose of technical development, the site PI will be responsible for seeking local approval for set-up scans on healthy volunteers. Where a site does not have such approval, sites can be provided with the SIGHT healthy volunteer PIS and consent form to provide to healthy volunteer(s). Where a healthy volunteer has provided informed consent for a setup scan at one site, should this volunteer undergo a scan at one or more other sites for setup purposes, a copy of the consent form can be provided to other sites.

Consent will be sought for the MRI set-up scan and for the arising data to be shared with the research teams at the Universities of East Anglia, Cambridge and Birmingham.

5.1.2.5.1 Incidental findings during set-up scans

Heathy volunteers will be made aware that the setup scans will not be reviewed by radiologist although there is the possibility for incidental findings to be identified. The volunteer will be asked to provide consent to be advised of any incidental findings, and ideally to provide GPs details, although this will be optional. Volunteers will be advised that their GP will only be contacted in the event of an incidental finding.

5.2 Site approval and activation

On receipt of the signed investigator statement, approved delegation of responsibilities log and staff contact details, written confirmation will be sent to the site PI. The trial manager or delegate will notify the PI in writing of the plans for site initiation. Sites will not be permitted to recruit any participants until a letter for activation has been issued. The Trial Manager or delegate will be responsible for issuing this after a green light to recruit process has been completed.

The site must conduct the trial in compliance with the protocol as agreed by the Sponsor, HRA, by the regulatory authorities (as appropriate), and which was given favourable opinion by the Research Ethics Committee (REC). The PI or delegate must document and explain any deviation from the approved protocol and communicate this to the trial team at NCTU.

A list of active sites may be obtained from the SIGHT Trial team.

5.3 Participants

5.3.1 Eligibility Criteria

206 participants will be recruited from NHS stroke units by RDN staff or clinicians in the stroke service from either acute or community hospital settings. The eligibility criteria have been informed by our pilot c-SIGHT feasibility trial and are designed to be as inclusive as possible to match our trial sample to the 'real' clinical population for whom SIGHT would be suitable if it were available as part of NHS routine stroke rehabilitation.

Patient information sheets and informed consent forms are adapted for people with aphasia post-stroke and those without capacity. We will use aphasia friendly documents as they facilitate maximum engagement of participants with visual, cognitive and/or communication impairments which has proved to be most efficient for both patients and staff as seen in our previous work [17]. We will also implement consent by personal consultee for those without mental capacity to consent. This will be implemented in response to feedback from PPI representatives in our c-SIGHT feasibility trial and follows other stroke trials (such as SPATIAL - the largest RCT on spatial neglect in the UK to date [56]). Consenting patients will be asked to identify a partner, relative or friend who is in regular contact with the participant. If the patient loses capacity, consultee assent will be sought from the partner, relative or friend for the remaining outcome measures.

Patients who lack capacity were included in our c-SIGHT and SPATIAL feasibility trials and we did not find specific compliance issues in relation to the intervention or to OT in general. Including stroke survivors without capacity will increase recruitment of people with spatial neglect who tend to have more significant cognitive issues than other stroke survivors and have so far been excluded from taking part in rehabilitation trials. In addition, our budget also includes the cost of translation services for people who cannot communicate in the English language. Finally, SIGHT intervention will be delivered either in acute or community hospital settings. Together, these procedures will ensure that our trial is directed at all stroke survivors regardless of level of stroke severity, disability and communication ability. Some attrition is anticipated, therefore competitive recruitment across sites will continue until 206 participants has been reached and the trial team will monitor recruitment figures to ensure recruitment will be stopped.

Potential participants and/or consultees will be identified by staff members familiar with the trial and the relevant departments in NHS institutions. Identification will utilise paper or electronic hospital records. Staff will check the clinical information and check eligibility criteria against the study criteria. Stroke research nurses and study coordinators will assist in patient recruitment and receiving consent as well as collection of baseline data.

To increase accessibility to the study, poster, leaflets, or audio/video may be used to inform participants of the trial offering a variety of ways to show prospective participants information regarding SIGHT.

Potential participants and/or consultees may be provided with study information either in person or by post/email. All potential participants will be offered the opportunity to discuss the advantages and disadvantages of study participation with a member of the research team and/or their physician before providing consent.

